6.4. M0- INTENTION TO TREAT POPULATION (M0-ITT)

The M0-Intention To Treat (M0-ITT) population consists of all subjects from ITT with at least 1 eligible complete LV Vector Tests at M0 visit.

LEVEA – Statistical Analysis Plan

6.5. M1- INTENTION TO TREAT POPULATION (M1-ITT)

The M1-Intention To Treat (M1-ITT) population consists of all subjects from ITT with at least 1 eligible complete LV Vector Tests at M1 visit.

6.6. ANCILLARY POPULATION (AP)

The Ancillary Population (AP) consists of all subjects in IP with at least one right ventricular pacing electrogram collected at the M0 or M1 visit.

6.7. PER-PROTOCOL POPULATION (PP)

The per-protocol population consists of all subjects in the EP who do not have any major protocol deviation (as classified in the eCRF) that could impact the interpretation of the primary analyses conducted on ITT.

The major protocol deviations will be identified as follows:

- Manual: These major protocol deviations will be identified at the time of the final data review meeting by means of listings provided by Global Biometrics. The identification of the major protocol deviations will be conducted by Data review team.

7. DISPOSITION

7.1. SUBJECT DISPOSITION

The number and percentage of subjects in each analysis population defined in Section 7 will be presented. The percentage will be calculated based on IP.

Disposition of subjects will be presented on IP.

The following summaries will be provided (% based on the total number of IP subjects):

- Number (%) of subjects who are included in the study
- Number (%) of subjects who had completed Inclusion, M0 and M1 visits.
- Number (%) along with reasons, of subjects who discontinued the study (based on Termination page) between Inclusion and M0 visits, between M0 and M1 visits, and after M1 visit.
- Number (%) of subjects who are in IP, EP, ITT, M0-ITT, M1-ITT, AP, PP

7.2. PROTOCOL DEVIATIONS

Major protocol deviations will be analyzed based on IP, ITT and M0-ITT, M1-ITT and information will be taken from “Protocol Deviation” page in eCRF.

- The number (%) of subjects by deviation category (description)

The protocol deviations leading to exclusion from analysis sets will be tabulated separately.

All (major and minor) protocol deviations will be listed.

8. DEMOGRAPHICS AND OTHER BASELINE CHARACTERISTICS

8.1. SUBJECT DEMOGRAPHICS

Subject demographics will be presented on the IP.

This analysis will include the following:

- Age (Years)
- Gender (Male/Female)
- Height (in m)
- Weight (in kg)
- Body Mass Index (BMI-kg/m²)
- NYHA

8.2. IMPLANT CHARACTERISTICS

The following implant characteristics will be analyzed by means of summary statistics in the IP analysis population.

- i. Pulse generator Manufacturer - Number and percentage of subjects with either of the three
 - o Platinium CRT-D SONR, 1811
 - o Platinium CRT-D SONR, 1841
 - o Platinium CRT-D SONR, 1844
- ii. RA Lead Manufacturer – Number and percentage of subjects with one of the following RA lead manufacturer:
 - o SORIN
 - o Medtronic
 - o St Jude Medical
 - o Boston Scientific
 - o Biotronik
 - o Other

LEVEA – Statistical Analysis Plan

- iii. RV Lead Manufacturer – Number and percentage of subjects with one of the following RV lead manufacturer:
 - o SORIN
 - o Medtronic
 - o St Jude Medical
 - o Boston Scientific
 - o Biotronik
 - o Other

- iv. LV Lead Manufacturer – Number and percentage of subjects with one of the following LV lead manufacturer:
 - o SORIN
 - o Medtronic
 - o St Jude Medical
 - o Boston Scientific
 - o Biotronik
 - o Other

Summary statistics for the following variables will be provided on EP for all visits

- i. Summary statistics for RA and RV Pacing Threshold
- ii. Summary statistics for RA and RV Pacing Width
- iii. Summary statistics for LV Pacing Threshold
- iv. Summary statistics for LV Pacing Width
- v. Summary statistics for RA, RV, LV impedances
- vi. Summary statistics for RA, RV sensing amplitudes

8.3. MEDICAL HISTORY

Medical history will be summarized in IP. Descriptive statistics (mean, median, standard deviation, 95% CI of mean, Q1, Q3, minimum and maximum) will be presented for continuous variables. The number and percentage of subjects in each category will be presented for categorical variables. The number and percentage of subjects with missing data will be provided.

8.4. PRIOR AND CONCOMITANT MEDICATION

Medications at enrollment and at termination visit obtained from the Medication eCRF page will be presented for IP. Only Cardiovascular medications are recorded.

Prior and Concomitant Medications will be summarized and sorted alphabetically. The number (and percentage) of subjects will be displayed for each kind of medication.

LEVEA – Statistical Analysis Plan

Medications will be summarized showing number and percentage of subjects with at least one medication at enrollment and at each visit (Inclusion, AE visits, Termination visit).

Medications will be considered as per coding by Safety officer.

9. PRIMARY EFFICACY ANALYSES

9.1. PRIMARY ENDPOINT ANALYSIS

9.1.1. PRIMARY ENDPOINT

The primary endpoint of the study is the success rate of “In-Clinic LVAT” test, that is the (Number of successes/Total Number of completed LV vector tests excluding the tests for which Manual tests are missing) of the “In-Clinic LVAT” feature.

For the primary endpoint, the evaluation is performed on 5 LV pacing vectors common to IS1 and IS4 leads:

Table 7: LV tests for Primary Endpoint

#	IS1 lead	IS4 lead
1	LVtip-LVring	LVtip1-LV2
2	LVtip-RVcoil	LVtip1-RVcoil
3	LVtip-CAN	LVtip1-CAN
4	LVring-RVcoil	LV2-RVcoil
5	LVring-CAN	LV2-CAN

Test will be evaluated at different LV pacing conditions: DDD A-test and VVI test. Among all the eligible complete LV Vector Tests collected, only those performed in DDD A-test with atrial overdrive pacing configuration (if available, otherwise in VVI) and with a manual LV threshold test performed in the same conditions (same pacing pulse width) and reported in the electronic Case Report Form (eCRF) will be retained. In case several LV Vector Tests were eligible with the same LV pacing vector, for the same subject, on 2 different visits, only M0 data will be considered.

The primary analysis is based on manual tests which are non-missing and for which complete LV Vector Tests are provided by the algorithm and collected at M0. If data at M0 is unavailable, then corresponding data collected at M1 will be considered.

To summarise, the following table mentions the adequate LV pacing configuration to be considered for the LV Vector test for the Primary Analysis:

Table 8: LV tests for Primary Analysis

Cases	Visit	LV pacing Configuration		Which one to use?
		DDDA-test	VVI test	

LEVEA – Statistical Analysis Plan

Cases	Visit	LV pacing Configuration		Which one to use?
		DDD-test	VVI test	
Case 1	M0	Available	Available	Use DDD A-test
Case 2	M0	Available	Unavailable	Use DDD A-test
Case 3	M0	Unavailable	Available	Use VVI test
Case 4	M0	Unavailable	Unavailable	Go to M1
	M1	Will be considered only for Case 4		
Case 5	M1	Available	Available	Use DDD A-test
Case 6	M1	Available	Unavailable	Use DDD A-test
Case 7	M1	Unavailable	Available	Use VVI test
Case 8	M1	Unavailable	Unavailable	Unavailable

9.1.2. STATISTICAL TEST OF PRIMARY ENDPOINT

The Null hypothesis: Success rate of the “In-Clinic LVAT” feature $< 90\%$.

The alternative hypothesis: Success rate of the “In-Clinic LVAT” feature $\geq 90\%$.

Each LV vector test will be categorized as a success if the automatic and manual LV threshold test has an equivalent LV threshold value, and failure otherwise. The definition of an equivalent LV threshold value is provided above in Table 4.

The success rate of “In-Clinic LVAT” test is defined as: Number of successes/Total Number of completed LV vector tests (excluding the tests for which Manual test is missing).

A one-sided exact binomial test for proportion at 2.5% level of significance (alpha) will be performed to test the null hypothesis for the primary endpoint. The null hypothesis will be rejected if the p-value is less than 0.025.

The estimate of success rate and 95% exact CI (Clopper & Pearson, 1934) will be presented.

LEVEA – Statistical Analysis Plan

DECOMPOSITION OF PRIMARY ENDPOINT SUCCESS RATE BY LV VECTOR AND BY CONFIGURATION

Total number of completed and successful LV vector tests considered for the Primary Analysis will be presented by:

- i. LV vector tests considered with DDD A-test LV pacing configuration at M0 visit. The break up of the five LV vectors will also be presented.
- ii. LV vector tests considered with VVI test LV pacing configuration at M0 visit. The break up of the five LV vectors will also be presented.
- iii. LV vector tests considered with DDD A-test LV pacing configuration at M1 visit. The break up of the five LV vectors will also be presented.
- iv. LV vector tests considered with VVI test LV pacing configuration at M1 visit. The break up of the five LV vectors will also be presented.

Only those LV tests will be considered for which manual tests are non-missing. For number of LV vector tests “completed”, the percentage will be calculated based on ITT.

For number of LV vector tests “Successful”, the percentage calculated based on number of LV vector tests “completed”.

All LV vector test results will be listed.

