4.1.2. Primary endpoint

The primary endpoint of the study is the success rate of “In-Clinic LVAT” test.

The success is defined by a LV threshold value identified automatically by “In-Clinic LVAT” feature equivalent to the manual threshold test value performed by physician on at least 90% among complete tests (performance goal).

For the primary endpoint, the evaluation is performed on 5 LV pacing vectors common to IS1 and IS4 leads: LV bipolar, LVring-RVcoil, LVtip-can, LVtip-RVcoil, and LVring-can pacing vectors. Test will be evaluated at different pacing conditions: DDD A-test and VVI. Results will be analyzed irrespective of the type of lead used (bipolar or quadripolar) and in any test configuration (DDD A-test or VVI).

An equivalent LV threshold value is defined as the same value of automatic and manual LV threshold tests, with a flexibility of ± 2 steps (meaning $\pm 0.5V$ if threshold $< 2.5V$, else $\pm 1V$ as measured in 2 consecutive cardiac cycles). A margin of ± 2 steps is accepted because of the variability of the threshold, and due to the design of the algorithm.

Among all the eligible complete LV Vector Tests collected, only those performed in DDD A-test with atrial overdrive pacing configuration (if available, otherwise in VVI) and with a manual LV threshold test performed in the same conditions and reported in the electronic Case Report Form (eCRF) will be retained. Only one LV Vector Test per LV pacing vector per subject will be analyzed.

In case several LV Vector Tests were eligible with the same LV pacing vector, for the same subject, on 2 different follow-ups, only M0 data will be considered.

The primary analysis is based on at least 231 complete LV Vector Tests provided by the algorithm and collected at M0. If data at M0 is unavailable, then corresponding data collected at M1 will be considered.

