5.7. LV VECTOR TEST

“In-Clinic LVAT” test is composed of several LV Vector Tests, each corresponding to a selected LV pacing vector (out of a possible 14 LV vectors).

The following definitions apply when performed on the same subject, with the same pulse width (in order to be comparable, the pacing width between automatic tests (any of them) and manual test needs to be strictly similar), on the same LV pacing vector and at the same visit:

- Attempted LV Vector test: If a LV Vector test, corresponding to an available LV pacing vector, was not launched during a visit then the LV Vector test will be classified as “Not Attempted”, and otherwise “Attempted”. That is, if an LV Vector test which was launched and neither interrupted nor aborted, it will be considered as “Attempted”.
- A complete LV Vector Test: test was performed (not aborted or interrupted) and a threshold value is provided by the algorithm. A LV Vector test resulting to a “no capture or high pacing threshold > 5V” at starting amplitude is considered as a complete LV Vector test. If a test was not aborted/neither interrupted and has no value, then the test will be considered as attempted but not completed.

The conditions for Attempted, Aborted and Interrupted can be further understood from the following table:

Table 3: Conditions for Completed LV test

Attempted	Aborted = Yes or No	Interrupted = Yes or No	Complete	Threshold Value
No	NA*			
Yes	Yes	No	No	Missing
Yes	No	Yes	No	Missing
Yes	No	No	Yes	Not missing

* Corresponding data is missing.

- A successful LV Vector Test: threshold value provided automatically by the algorithm is equivalent to the manual threshold test done by the physician among the complete LV Vector Tests.

LEVEA – Statistical Analysis Plan

An LV threshold value obtained from the device algorithm (automatic) will be considered as equivalent to the manual threshold value if the automatic and manual LV threshold tests has the same value, with the same pacing pulse width, with a flexibility of ± 2 steps (meaning $\pm 0.5V$ if threshold $< 2.5V$, else $\pm 1V$). A margin of ± 2 steps is accepted because of the variability of the threshold, and due to the design of the algorithm.

The equivalent range for the Algorithm for a Manual threshold is provided in the table below:

Table 4: Equivalent ranges for Successful LV tests (Manual vs. Algorithm)

Manual Threshold value obtained (in V)	Equivalent Range of the Algorithm (Automatic threshold) (in V)
7	>5
6	>5
5	>4.0

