4.5	3.5-5.0
4.0	3.0-5.0
3.5	2.5 - 4.5
3.0	2.25 - 4.0
2.75	2.25 -3.5
2.5	2- 3.5
2.25	1.75-3
2.0	1.5-2.5
1.75	1.25-2.25
1.5	1.0-2.0
1.25	0.75-1.75
1	0.5-1.5
0.75	0.25-1.25
0.5	0.25-1.0

LEVEA – Statistical Analysis Plan

0.25	0.25-0.75
------	-----------

Note: if an LV test is reported to be done, but no manual threshold value is present, it will be imputed as “Missing”.

- A failed LV Vector Test: threshold value provided automatically by the algorithm is not equivalent to the manual threshold test done by the physician or adjudicated by the independent reviewer among the complete LV Vector Tests.

As values determined by the algorithm are not displayed on the programmer screen, data are stored in the electronic Real-Time Data (RTD) files that are loaded in the electronic Case Report Form (eCRF) in order to be extracted by the sponsor.

- Diagnostic accuracy is defined as an accurate adjudication by an independent reviewer of LV threshold value provided by the algorithm. The adjudication is based on capture and loss of capture analysis on electrogram strips recorded and stored during “In-Clinic LVAT” tests. The LV threshold value provided by the algorithm compared to the reviewer adjudication is considered accurate if the difference is within ± 1 step.

The “Accurate” range for the Independent Reviewer for a Algorithm (Automatic) threshold is provided in the table below:

Table 5: Equivalent ranges for Accurate LV tests
(Algorithm vs. Independent reviewer)

Threshold value obtained with the algorithm (Automatic) (in V)	Accurate Range (Independent reviewer)
>5	>5
5.0	>4.5
4.5	4.0-5.0
4.0	3.5-4.5
3.5	3.0-4.0
3.0	2.5-3.5
2.5	2.25- 3
2.25	2.0-2.5
2.0	1.75-2.25
1.75	1.5-2.0

LEVEA – Statistical Analysis Plan

1.5	1.25-1.75
1.25	1.0-1.5
1.0	0.75-1.25
0.75	0.5-1.0
0.5	0.25-0.75
0.25	0.25-0.5

- Assessment of LV pacing threshold underestimation: comparison to manual LV threshold value will be performed by comparing manual and automatic LV threshold values at each visit. An underestimated LV threshold value of “In-Clinic LVAT” feature is defined as a value result more than 2 steps below the LV threshold measured manually (meaning -0.5V if threshold<2.5V, else -1V as measured).

Table 6: Ranges for Under-estimated LV tests
(Manual vs. Algorithm)

Manual Threshold value obtained (in V)	Under-estimated if - Automatic threshold value (in V)
7	< 5
6	<4.5
5	< 4.0
4.5	<3.5
4.0	<3.0
3.5	<2.5
3.0	<2.25
2.75	<2.25
2.5	<2.0
2.25	<1.75
2.0	<1.5
1.75	<1.25

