10. SECONDARY EFFICACY ANALYSES

Secondary and Ancillary endpoints will be assessed at all visits using descriptive statistics. Point estimates and exact CI (Clopper & Pearson, 1934) will be presented wherever possible.

Whenever a Statistical test is performed for a Secondary Endpoint, it is of hypothesis generating and descriptive in nature.

10.1. ASSESSMENT OF DIAGNOSTIC ACCURACY OF “IN-CLINIC LVAT” TEST AT M0 VISIT: INDEPENDENT REVIEWER VALIDATION OF LV THRESHOLD VALUE PROVIDED BY ALGORITHM

This endpoint is the number of accurate determination of the LV pacing threshold value provided by the algorithm feature and an independent reviewer, on all LV pacing vectors and all pacing configurations available at M0 visit.

Diagnostic accuracy is defined as an accurate adjudication by an independent reviewer of LV threshold value provided by the algorithm. The adjudication is based on capture and loss of capture analysis on electrogram strips recorded and stored during “In-Clinic LVAT” tests. The LV threshold value provided by the algorithm compared to the reviewer adjudication is considered accurate if the difference is within ± 1 step (meaning ± 0.25 V if threshold < 2.5V, else ± 0.5 V as measured). The definition of an Accurate LV threshold value is provided above in Table 5.

In case the algorithm and the reviewer adjudication provide both a LV threshold value equal to “>5V” (the LV vector test has resulted in “no capture” or “threshold value higher than 5V at starting amplitude), the LV threshold value is considered accurate. Number and percentages of “accurate” and “inaccurate” matches will be presented along with the exact 95% CI (Clopper & Pearson, 1934).

This analysis will be performed on M0-ITT population.

Decomposition of Diagnostic Accuracy by LV Vector and by LV pacing configuration

Total number of attempted, completed, and accurate LV vector tests will be presented by LV vector for each LV pacing configuration.

For the LV tests performed for subjects with either IS1 and IS4 leads (six LV vectors common to IS1 and IS4), the percentage for the number of LV vector tests “attempted”, will be calculated based on the number subjects implanted with either IS1 and IS4 leads.

For the LV tests performed for patients with IS4 leads (eight LV vectors pertaining only to IS4), the percentage for the number of LV vector tests “attempted”, will be calculated based on the number of patients implanted with IS4 lead.

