11. SECONDARY SAFETY ANALYSES

11.1. ASSESSMENT OF THE DEVICE CHARACTERISTICS IN TERMS OF SAFETY AND DEVICE DEFICIENCY

- A. Serious adverse device events and device deficiencies will be collected during each subject visit. Confirmation of absence of USADE during “In-Clinic LVAT” tests will be evaluated by analyzing all SAEs and device deficiencies (DD) collected at each visit.

This secondary endpoint will be based on IP.

- B. Algorithm characteristic: Underestimated Assessments

Assessment of LV pacing threshold underestimation: comparison to manual LV threshold value will be performed by comparing manual and automatic LV threshold values at each visit. An underestimated LV threshold value of “In-Clinic LVAT” feature is defined as a value result more than 2 steps below the LV threshold measured manually (meaning -0.5V if threshold<2.5V, else -1V as measured) . Please see table 6.

LEVEA – Statistical Analysis Plan

Number and percentages of “underestimated” assessments will be presented along with the exact 95% CI (Clopper & Pearson, 1934) by M0 and M1 visit. Only subjects with non-missing manual data will be considered.

The reasons for LV pacing threshold underestimation at M0 visit will be presented as table and listing. The missing reasons (if any) for underestimation will be presented as “Not available”. For the table, the number and percentages of the reasons will be presented with the denominator of the percentages based on the total number of LV pacing threshold underestimated.

Total number of attempted, completed,, Underestimated LV vector tests will be presented by LV vector for each LV pacing configuration by visit.

For the LV tests performed for patients with either IS1 and IS4 leads (six LV vectors common to IS1 and IS4) , the percentage for the number of LV vector tests “attempted”, will be calculated based on the number of patients implanted with either IS1 and IS4 leads.

For the LV tests performed for patients with IS4 leads (eight LV vectors pertaining only to IS4), the percentage for the number of LV vector tests “attempted”, will be calculated based on the number of patients implanted with IS4 lead.

For number of LV vector tests “completed”, the percentage will be calculated based on the number of LV vector tests attempted.

For number of LV vector tests “Underestimated”, the percentage calculated based on number of Complete LV vector tests .

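### The margin text, its volt meaning, Table 4 (primary success) and Table 6 (underestimation) in SAP 5.7 are not one rule, and they conflict most plainly at manual 5 to 7 V

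*SAP*

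**What the plan says.** Protocol 4.1.2 begins its definition with "An equivalent LV threshold value is defined as the same value of automatic and manual LV threshold tests" and allows two steps either way, explained as 0.5 V when the threshold is under 2.5 V and 1 V otherwise. SAP 5.7 repeats this margin and turns it into Table 4, "Equivalent ranges for Successful LV tests (Manual vs. Algorithm". For the primary test, SAP 9.1.2 points to the table: "The definition of an equivalent LV threshold value is provided above in Table 4".

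The underestimation endpoint uses the same margin in the downward direction. SAP 5.7 defines it as "a value result more than 2 steps below the LV threshold measured manually" and implements it in Table 6. SAP 11.1 B repeats the definition with its volt meaning: "more than 2 steps below the LV threshold measured manually (meaning -0.5V if threshold<2.5V, else -1V as measured".

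For comparison with the independent reviewer (±1 step), SAP 10.1 says "The definition of an Accurate LV threshold value is provided above in Table 5".

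Two other sections bear on the top of the range. SAP 13.1 says every test starts at 5 V and that a higher threshold, or no capture, is coded as >5 V. SAP 5.7 says such a result "at starting amplitude is considered as a complete LV Vector test". SAP 13.5 lists the 15 numeric values the algorithm can return: 0.25 to 2.50 V by 0.25, then 3.0 to 5.0 V by 0.5. SAP 3.1 records no change from the protocol.

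**The concern.** If Tables 4 and 6 apply the same two-step margin, a result too low to be equivalent must be an underestimate, and the reverse. If the volt gloss is what two steps means, it must give the same answer as the tables. Neither holds.

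One manual/algorithm pair can then be a low failure on the primary endpoint and not an underestimate on the safety endpoint. The two endpoints use different populations and test selections, so their totals would differ anyway, but the classification of a given pair should not. Someone scoring by the protocol's volt meaning will also reach different results from someone using the SAP table, on an endpoint tested against a fixed 90% goal.

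**Working it through.** Pairs are written manual/algorithm in volts.

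**Inputs.** The 18 manual rows of Tables 4 and 6 (SAP 5.7), crossed with the 15 numeric algorithm values in SAP 13.5. Outputs coded >5 are left out because their distance is undefined. The sample-size inputs come from SAP 2.3: null 90%, expected 95%, one-sided alpha 2.5%, power 80%.

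**The plan's own figure.** With an exact binomial test at n = 231, 217 or more successes (14 or fewer failures) reject: P(failures ≤ 14 | 10%) = 0.0239. Power is P(failures ≤ 14 | 5%) = 0.816. The 231 tests are reproduced. 231/5 = 46.2 gives 47 subjects, and 47/0.8 = 58.75 gives 59.

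**Limits at the top of the tables.**

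| Manual (V) | Table 4 success | Table 6 underestimated |
|---|---|---|
| 7 | >5 | <5 |
| 6 | >5 | <4.5 |
| 5 | >4.0 | <4.0 |
| 4.5 | 3.5 to 5.0 | <3.5 |
| 4.0 | 3.0 to 5.0 | <3.0 |

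- 5/4.0: 5 − 4.0 = 1 V, inside the gloss, but Table 4 fails it.
- 6/5.0: 6 − 5.0 = 1 V, inside the gloss, but Table 4 fails it.
- The 4.5 and 4.0 rows accept a value exactly 1 V low (3.5 and 3.0).

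**Table 4 against Table 6.** Exactly four pairs fail low in Table 4 and are not underestimated in Table 6: 5/4.0, 6/4.5, 6/5.0 and 7/5.0. Of these, 6/4.5 (1.5 V low) and 7/5.0 (2 V low) are also beyond the −1 V gloss given with Table 6. No pair is both a Table 4 success and a Table 6 underestimate.

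**Table 4 against the volt gloss.** The gloss does not say which test's threshold sets the margin.

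- Manual value: 8 pairs differ. Table 4 is stricter at 2.5/1.5, 2.5/1.75, 2.75/1.75, 2.75/2.0, 3.0/2.0, 5/4.0 and 6/5.0, and more lenient at 2.25/3.0.
- Algorithm value: 6 pairs differ. Table 4 is stricter at 1.5/2.5, 1.75/2.5, 2.0/3.0, 5/4.0 and 6/5.0, and more lenient at 3.0/2.25.

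Only 5/4.0 and 6/5.0 are in both lists.

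**Tables against a step count.**

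- SAP 13.5 ladder only (15 × 15 = 225 pairs): Table 4 departs at 5/4.0, Table 6 nowhere.
- 6 and 7 V assumed as rungs, 2.75 V counted only in its own row: Table 4 departs at the four pairs above (all stricter), Table 6 nowhere.
- 2.75 V as a rung throughout: Table 4 departs at 8, the same four plus four more lenient (2.25/3.0, 2.5/3.5, 3.0/2.25, 3.5/2.5). Table 6 departs at 2 (3.0/2.25, 3.5/2.5).

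**Table 5.** An algorithm value of 5.0 requires a reviewer value above 4.5, so 4.5, one step away, is inaccurate. The reverse, algorithm 4.5 with reviewer 5.0, is accurate.

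**Effect on the primary test.** At n = 231, P(failures ≤ 14 | 10%) = 0.0239 rejects and P(failures ≤ 15 | 10%) = 0.0418 does not. As an illustration only, take 95% true success before reclassification and move an assumed share of all tests to failure:

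| Share moved | True success | Power |
|---|---|---|
| 0% | 95% | 82% |
| 0.1% | 94.9% | 80% |
| 0.5% | 94.5% | 71% |
| 1% | 94% | 59% |
| 2% | 93% | 34% |

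**The case against.** **A lost symbol.** The strict limits at 5 to 7 V may be ≥ signs lost in typing or in text extraction. That would explain 5/4.0, 6/5.0, 7/5.0 and the Table 5 cell. It would not explain 6/4.5 or the six pairs at manual 2.25 to 3.0 V, and Table 4 would then accept 7/5.0, which is 2 V low.

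**The 5 V start.** Because tests start at 5 V, >5 is the expected output when the manual value is 6 or 7 V, and requiring it may be deliberate. That is plausible. But the SAP does not give it as the reason, Table 6 does not follow it, and it does not explain 5/4.0. Step distances above 5 V do rest on assumed rungs; the conflict between Tables 4 and 6 does not.

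**Table 4 governs.** SAP 9.1.2 gives the primary analysis a single lookup, and at manual 2.25 to 3.0 V Tables 4 and 6 agree with each other and, with 2.75 V counted only in its own row, with two steps. So for those six pairs it is the volt wording that fails to match where the step size changes. This stands. But that wording is also in the protocol, and the SAP declares no change.

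**Size.** High thresholds may be rare, underestimation is descriptive, and the effect could be nil. This also stands: the documents give no frequency for any affected cell, and the power figures are illustrative.

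**Conclusion.** The point holds. One stated margin is implemented as rules that disagree: 4 pairs between Tables 4 and 6, and 8 pairs (6 on the other reading) between Table 4 and the volt gloss. The failures of 5/4.0 and 6/5.0 contradict the stated volts whichever test sets the margin.

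For numeric outputs the 5 to 7 V departures are all stricter than the gloss or the step count, so they cost power and do not make a false claim of meeting 90% easier. Outputs of >5 were not assessed: Table 4 accepts them at manual 5, 6 and 7 V with no upper bound and rejects them at 4.5 V and below. The share of tests in the affected cells is unknown. The matter should be fixed because it concerns how primary success is scored and one test can decide the result at the boundary. This assessment does not say which limits are right.

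**What to change.** - Reconcile the margin text, the volt gloss and Tables 4, 5 and 6 to one rule on one explicit voltage ladder.
- State which test's threshold sets the margin, and how 2.75 V, values above 5 V and >5 outputs are counted.
- Make every complete pair with a manual value exactly one of equivalent, underestimated or overestimated, and state and justify any exception at manual 5 to 7 V.
- Record the change and its rationale in SAP 3.1. Protocol section 8 requires this for relevant major changes, and the scoring of primary success should be treated as one.
- Settle the rule without reference to results. The algorithm extract named in SAP 17.8 carries the date 20180112, before SAP 1.0 (19Feb2018). The file name does not show that anyone had compared results, but it is reason for care.
- Report the primary success rate under Table 4 as printed and under the reconciled rule, and say beforehand which one decides the test.

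The cost is a few table edits, the margin wording, one entry in SAP 3.1 and one sensitivity line. The 231-test target does not change.
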